4.1. Estimand

The primary estimand is the change from baseline at Week 8 in HVA for subjects with AADC deficiency who meet the entry criteria for the study and received any amount of the study drug.

4.2. Interim Analysis

No interim analysis to decide whether to continue the study will be performed. However, for this open-label study, data summary may be performed while study is ongoing for Regulatory purpose.

4.3. Data Definition and Analysis Issues

The following derivations will be used in this study:

Baseline

The last non-missing data collected prior to drug administration is the study baseline.

Study Day

- For assessments done on or after date of study drug administration:
Study day = Date of assessment – date of study drug administration + 1
- For assessments done before date of study drug administration:
Study day = Date of assessment – date of study drug administration

Duration of follow-up

Duration of follow-up = last visit date recorded – date of study drug administration + 1

4.3.1. Handling of Dropouts or Missing Data

Missing data due to missed visits or withdrawal or death will not be imputed.

In administering PDMS-2, the following instructions were provided in the PDMS-2 Manual:

- **Entry Points:** The entry points are marked on each subtest in the Examiner Record Booklet. The entry points were determined empirically to allow the examiner to begin testing on an item that 75% of children in the normative sample at that age passed. When testing children with known disabilities, the examiner should use clinical judgement to determine the most appropriate entry point.
- **Basal Level:** The basal level is established when the child receives a score of 2 on 3 items in a row. The last three 2s before the 1 or 2 become the basal level. The examiner begins testing with the entry point item. If the child does not score 2 on each of the first 3 items administered, that is, if the child scores 0 or 1 on any of the first 3 items administered starting from the entry point, the examiner should test backward until the child scores 2 on 3 items in a row. This is the basal level. All items below the basal level are scored 2.
- **Ceiling Level:** Once the basal level has been established, the examiner administers progressively more difficult items until a ceiling is established. The ceiling is established when the child scores 0 on each of 3 items in a row. After the ceiling has been established, testing is discontinued. All items above the ceiling are scored 0.

If a score of 2 for items below basal level or score of 0 for items above ceiling are not entered in the evaluation, they will be filled in according to the instruction of the manual.

For each visit and subtest:

- An “observed” value is an item with a recorded value in a subtest (e.g., 0, 1, 2 and Not Evaluated).
- Within a subtest, all items prior to the first item with an “observed” score are considered “Basal” and are assigned the score of 2.
- An empty item in a subtest surrounded by “observed” values (e.g., there are “observed” values prior to the item and after the item), the value is to be left empty and considered “observed”.
- All items after the last recorded value in a subtest, or “observed” value (e.g., 0, 1, 2 and “Not Evaluated”), are considered “Ceiling” values and are assigned a score of 0).

The above will not affect summary and analyses of the study results because total scores collected in the case report form for each subtest are provided by the study site, and the study site included a score of 2 for all the basal items in the calculations of total score. The individual scores filled according to the manual as described above are only used to derive variables for motor milestone achievements.

For analysis and summary of motor milestones achievement, the following 3 terminologies will be used:

- Assessed: Item of interest is “observed” as defined above. This does not include score=0 assigned after reaching ceiling;

- Emerging: Item of interest has a Score =1;
- Mastery: Item of interest has a Score=2.

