7.3.2. Peabody Developmental Motor Scale, Second Edition

The PDMS-2 is a validated instrument used to measure motor skills and developmental milestone achievement in infants and children ([Folio 2000](#)).

To optimize testing duration in this pediatric population, for all subtests except for Reflexes, the PDMS-2 administrator may begin testing at an entry point, which is a predetermined item that most of children in the healthy population are able to achieve at a given age. A basal level will then be determined, which is the point at which the subject achieves a score of 2 on 3 consecutive skill items prior to achieving a 0 or 1 score on a skill item; all items below the basal level are scored as 2. Finally, a ceiling level is determined, which is the point at which the subject achieves a score of 0 on 3 consecutive skill items. All items above the ceiling are scored as 0, and the testing will be discontinued.

The PDMS-2 instrument is scored by a qualified physiotherapist. Each skill item is assessed as a simple, 3-level scoring system as a consistent way of describing the child's achievement of a particular motor skill, as listed below:

0 = the skill is not met

1 = the skill is emerging and shows a clear resemblance to mastery of the skill item

2 = the child is mastering the motor skill

A composite Gross Motor Quotient will be calculated from the scores on the Reflexes (8 skill items; age birth to 11 months), Stationary (30 skill items), Locomotion (89 skill items), and Object Manipulation (24 skill items; age 12 months and older) subscales. A composite Fine Motor Quotient will be calculated from the scores on the Grasping (26 skill items) and Visual Motor Integration (72 skill items) subscales. A Total Motor Quotient, which incorporates the results of both the Gross and Fine Motor Quotients, is considered the most complete evaluation of overall motor skills.

The PDMS-2 motor skill items assess key motor milestones of 1) full head control, 2) sitting unassisted, 3) standing with support, and 4) walking assisted, which were chosen for further statistical assessments as these were the key motor milestones used to define the natural history of patients with AADC deficiency ([Wassenberg 2017](#)). There are several components of each motor skill that become progressively more difficult. The PDMS-2 motor skill items that were used to assess motor milestones are described below:

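### The SAP's PDMS-2 fill rule credits untested items as 2 without checking for a basal, and its stated limit on filled scores conflicts with the six-item grasping score

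*SAP*

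**What the plan says.** SAP 4.3.1 summarises the manual. A basal is three 2s in a row; if any of the first three items is not a 2, the examiner tests backward until a basal is found; and "All items below the basal level are scored 2". Where those scores were not entered, "they will be filled in according to the instruction of the manual".

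The rules to be programmed follow. For items at the start of a subtest: "Within a subtest, all items prior to the first item with an “observed” score are considered “Basal” and are assigned the score of 2". An 'observed' "value is an item with a recorded value in a subtest (e.g., 0, 1, 2 and Not Evaluated"). Items after the last recorded one receive 0.

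The section then says that the fill does not affect results, because the site supplies the subtest totals, and that filled item scores are used only for motor milestone variables. It defines Mastery as a score of 2 on the item of interest.

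Protocol 7.3.2 places the basal at "the point at which the subject achieves a score of 2 on 3 consecutive skill items prior to achieving a 0 or 1 score", scores as 2 only the items below it, and treats an unscored milestone item as a fail.

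SAP 6.2.4 adds a secondary efficacy variable, the sum of Grasping items 7, 14, 15, 16, 17 and 18, summarised as observed score and change from baseline.

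**The concern.** The lead-in states the manual's condition and the rule beneath it omits that condition. A first recorded item that was failed, or not evaluated at all, is enough to score everything below it as 2. Milestones are derived from these filled scores.

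In such a record a false Mastery after treatment stays in the cumulative milestone table. One at baseline hides a later real gain from the summary of new milestones (SAP 6.2.3). Head control at score 2 also divides follow-up for the infection rates in SAP 6.2.11.

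The grasping problem is different and needs no departure from the manual. The score is built from individual items, and the SAP's limit on filled scores leaves it out.

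**Working it through.** The plan gives no figure to reproduce. The inputs are the fill rules (SAP 4.3.1), the basal rule (SAP 4.3.1 and Protocol 7.3.2), the milestone items (SAP Table 2: Stationary 5, 10, 11, 14; Locomotion 28, 31, 34, 35, 40, 44, 48), the grasping items (SAP 6.2.4), and the minimum of 3 subjects (SAP 2.4). The item records below are illustrations.

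**1. Manual followed and fully entered.** Backward testing stops at three 2s or at item 1. So either the three lowest recorded items are a basal, or nothing lies below the first recorded item. The SAP rule and a basal-checked rule must then agree. Stationary 3–5 = 2,2,2, 6 = 1, 7–9 = 0 gives 1 of 4 milestones under both. Stationary 12–14 = 2,2,2, 15 = 1, 16–18 = 0 gives 4 of 4 under both.

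**2. No basal recorded.** Milestones credited untested = number of Table 2 items numbered below the first recorded item.

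| Subtest | First recorded item | Credited by SAP rule | Credited with basal check |
|---|---|---|---|
| Stationary | 6–10 | 1 | 0 |
| Stationary | 11 | 2 | 0 |
| Stationary | 12–14 | 3 | 0 |
| Stationary | 15 or above | 4 of 4 | 0 |
| Locomotion | 28 or below | 0 | 0 |
| Locomotion | 29 | 1 | 0 |
| Locomotion | 37 | 4 | 0 |
| Locomotion | 51 or above | 7 of 7 | 0 |

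With Stationary 11–13 = 0,0,0 and blanks below, the SAP rule credits partial and full head control (items 5 and 10). Three items scored 0, 1 or 2 have 3³ = 27 patterns. The rule gives that credit for all 27, and only 2,2,2 is a basal. A lone 'Not Evaluated' at Stationary 19 yields 4 of 4. These are counts of patterns, not frequencies.

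**3. Size per affected child.** A milestone percentage moves by 1/3 = 33 points at 3 subjects, or 1/10 = 10 points at an assumed 10. PDMS-2 is scheduled at baseline and Weeks 24, 48, 72, 96, 156, 208 and 260 (Protocol Tables 1 to 3), so the gaps are 24, 24, 24, 24, 60, 52 and 52 weeks. Head control dated one PDMS-2 visit too early would move 24 to 60 weeks of that child's follow-up from 'prior' to 'after' in SAP 6.2.11.

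**4. Grasping, compliant record.** Take items 15–17 = 2,2,2, 18 = 1, 19–21 = 0, with easier items not entered.

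- With the fill, items 7, 14, 15, 16, 17, 18 give 2 + 2 + 2 + 2 + 2 + 1 = 11.
- From recorded items only, 2 + 2 + 2 + 1 = 7, with two of the six items missing.
- A basal starting at item 11, 15 or 18 leaves 1, 2 or 5 of the six items unfilled, which is 2, 4 or 10 of 12 points.
- At the other end, a ceiling at items 8–10 leaves items 14–18 blank. The sum is then missing if all six items are required.

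The site total cannot replace the items, because it covers the whole subtest: "Fine Motor Quotient will be calculated from the scores on the Grasping (26 skill items"). Items 1–14 all 2 total 14 × 2 = 28, with a six-item sum of 2 + 2 = 4. Items 1–12 all 2, 13 = 0 and 14–17 all 1 total 24 + 4 = 28, with a six-item sum of 2 + 4 = 6. The same total gives two different scores.

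**The case against.** The best defence is that the rule is shorthand for compliant data. A qualified physiotherapist administers the test, the manual requires backward testing, and the SAP twice ties the fill to the manual. For children with known disabilities it leaves the entry point to clinical judgement, so records starting at the high age-marked entry items cannot be presumed. Entry checks in the eCRF are not described in these documents and may catch the problem. The milestones are descriptive secondary summaries.

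Most of this stands, and it limits the milestone point to records that depart from the manual, at unknown frequency. It does not repair the rule. A programmer follows the specific instruction, and admitting 'Not Evaluated' as an anchor cannot be read as shorthand for a basal.

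On grasping, one can say that SAP 6.2.4 reports those items by the same Emerging and Mastery stages, so they count as milestones. That could cover the item counts. It does not cover the summed score or its change from baseline.

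A reader might also infer that a filled 2 fails to qualify as Mastery because the item was not 'Assessed'. SAP 4.3.1 settles this: Mastery depends on the score alone.

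**Conclusion.** The point holds in two parts. First, the fill rule omits the basal condition that the SAP and protocol both state, and it gives a wrong milestone whenever a record starts above a milestone item with no basal recorded. The size is 33 points per affected child at 3 subjects. It rests on such a record existing, which the documents neither show nor exclude. Second, the limit on filled scores conflicts with the grasping score even in compliant records, whenever 2s below the basal or 0s above the ceiling are not entered. Followed literally, the score is missing or too low.

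A reader might infer that the milestone results are generally inflated, or that the PDMS-2 totals or the primary endpoint are compromised. The documents do not support either. Compliant records are scored correctly, subtest totals come from the site, and HVA does not use the fill. Nor does every filled blank contradict the protocol: below a valid basal, the protocol itself scores 2.

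This should be corrected before the milestone and grasping tables are programmed, but it is not a threat to the trial's main conclusion.

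**What to change.** 1. In SAP 4.3.1, assign 2 to blank items only below a recorded basal of three consecutive 2s. State that 'Not Evaluated' cannot serve as the anchor.
2. Where no basal is recorded, query and list the record. If it stays unresolved, derive the milestone as not achieved, as Protocol 7.3.2 does for unscored items, and flag it in the listing. Leave the new-milestone rule in SAP 6.2.3 unchanged. A later success then counts as new, and the flag shows that the earlier status was unresolved.
3. Apply the same conditional fill to the SAP 6.2.4 items: 2 below a recorded basal and 0 above a recorded ceiling. Extend the 'only used' sentence to the grasping score, and confine the statement that results are unaffected to the site-supplied subtest totals.
4. Clerical: the SAP's "The last three 2s before the 1 or 2 become the basal level" should be reconciled with the protocol, which has 0 or 1.

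The cost is a few lines of SAP text and programming, with no new assessments. There will be a few more data queries, and a few milestones may be reported later or as not achieved.

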4.3.2. Adjustment for Covariates

When appropriate, baseline scores and age at the time of gene therapy will be used as covariates in the analysis model.

4.3.3. Multiple Comparisons and Multiplicity Adjustment

Not applicable.

4.4. Changes to Protocol Specified Analysis

No change.

5. SUBJECT DATA

5.1. Subject Disposition

A summary table for subject disposition will be provided for the number of subjects screened, number of screen failures, number dosed, number and percentage of subjects completed trial phase, extension phase, and long-term extension phase. Number of subjects and percentage of primary reason for discontinuation during each phase. Data listing for disposition information will be provided.

A summary table using descriptive statistics will be provided for duration of follow-up.

A separate listing for screen failure subjects will be provided.

5.2. Protocol Deviations

Protocol deviations will be recorded at the site in a deviation log separate from the clinical database. A data listing of all protocol deviations will be provided.

5.3. Demographic and Baseline Characteristics

A summary table will present descriptive statistics for age at onset, age at diagnosis, age at screening, age at gene therapy, height, weight, body mass index (BMI) and counts and percentages for sex, ethnicity, and race.

Listing for demographic characteristics including date of birth, age at onset, age at diagnosis, age at screening, age at gene therapy, date of treatment, sex, if female whether the subject is of childbearing potential, ethnicity, race, height, weight, and BMI will be provided.

Baseline assessments including genetic testing (method used in obtaining results, DDC gene variant allele 1 and DDC gene variant allele 2), CSF History (5-hydroxyindoleacetic acid, Homovanillic acid, 3-methoxy-4 hydroxyphenylglycol, Neopterin, Biopterin, 3-O-methyldopa, L-Dopa and 5-OH tryptophan), AADC Enzyme activity (Dopamine results, Dopamine range) will be presented.

A summary table of counts and percentages will be provided for genotype (homozygous and heterozygous).

5.4. Disease Characteristics

A summary of AADC-specific symptoms will be provided to show number and percentage of subjects with each symptom (floppiness, limb dystonia, stimulus-provoked dystonia, muscle tone, spontaneous movement, and muscle power), and the severity of symptom. A listing of AADC-specific symptoms will be provided.

5.5. Medical History

All medical conditions and surgical procedures will be classified by system organ class (SOC) and preferred term (PT) using the Medical Dictionary for Regulatory Activities (MedDRA) version 26.0 or most recent version.

The number and percent of subjects will be summarized for each SOC and PT. A subject will be counted only once for each SOC. A listing will be provided for medical history.

5.6. Prior and Concomitant Medications and Non-Drug Treatments

Prior and concomitant medications will be coded using World Health Organization (WHO) drug classifications version WHODrug B3 Global March 2023 or later.

The number and percentage of subjects will be summarized for each Anatomical, Therapeutic, and Chemical (ATC) level 3 term and PT. A subject will be counted only once for each ATC level term.

The reported name of drug or medication, ATC class, preferred name, indication, dose and units, frequency, route of administration, start date and end date, if not ongoing, will be listed.

5.7. Concomitant Procedure

All concomitant procedures will be classified by SOC and PT using MedDRA version 26.0 or later.

The number and percentage of subjects will be summarized for each SOC and PT. A subject will be counted only once for each SOC. The procedure, indication, and the procedure date will be listed.

5.8. Extent of Exposure

The total volume administered will be summarized using descriptive statistics. Counts and percentages will be provided for whether infusion was interrupted, and for the reason of interruption. Data collected for the study drug infusion record will be listed.

5.9. Intrasurgical MRI

A listing of intrasurgical MRI will be presented including the date it was performed, whether there was intracerebral hemorrhage, whether there was a leak during the study procedure, and the corresponding details if there is any.

5.10. Brain CT

Results (normal, clinically significantly abnormal and not clinically significantly abnormal) of brain CT performed pre-dose and post dose will be provided in a listing.

6. EFFICACY ANALYSIS

6.1. Primary Efficacy Analyses

The primary efficacy endpoint of observed values and change from baseline in HVA at Week 8 will be summarized using descriptive statistics. One-sample t-test will be performed for change and percentage changes from baseline to test whether the changes are statistically significantly different from 0.

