7.2. Primary Endpoints

7.2.1. HVA Levels

The precursor L-DOPA is decarboxylated by AADC to form dopamine. After action at the nerve synapse, dopamine is reabsorbed into the presynaptic nerve terminal where it can either be repackaged into vesicles for future neurotransmitter release or metabolized to HVA. In the presence of AADC deficiency, the HVA level in the CSF is very low or below the limit of detection due to the abnormally low dopamine production. Upon restoration of AADC activity, as premised with gene therapy, dopamine levels increase due to a now functioning *DDC* gene and the concentration of HVA in the CSF rises. Thus, HVA can serve as an acceptable measurement of dopamine production as a result of AADC activity ([Hyland 2006, Hyland 2007](#)).

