7.3.7. Measurement of 3-OMD and 5-HIAA

Similar to L-DOPA, the precursor 5-HTP is decarboxylated by AADC to form serotonin. After action at the nerve synapse, serotonin is reabsorbed into the presynaptic nerve terminal where it can either be repackaged into vesicles or metabolized 5-HIAA. In the presence of AADC deficiency, the 3-OMD level in the CSF is increased and the 5-HIAA level is very low or below the limits of detection due to the abnormally low serotonin production. Upon restoration of AADC activity, concentrations of 3-OMD levels decrease in the CSF and 5-HIAA rise ([Hyland 2006](#), [Hyland 2007](#)).

Neurotransmitter metabolites will be quantified following isocratic, reversed phase high performance liquid chromatography separation and coulometric electrochemical oxidation using EZChrom software.

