8. STATISTICAL METHODS AND DATA ANALYSIS

8.1. Sample Size Determination

This study has no formal statistical hypothesis testing, and the sample size is not based on statistical consideration. A minimum of 3 subjects is planned to assess HVA level at Week 8 and safety of the SmartFlow MR-compatible ventricular cannula for administering eladocagene exuparvovec to pediatric subjects.

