8.3.2. Analysis of Primary Endpoints

8.3.2.1. Primary Efficacy Analysis

Observed values and change from baseline in HVA at Week 8 will be summarized using descriptive statistics (count, mean, standard deviation, median, minimum, and maximum) for each timepoint.

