4. GENERAL CONSIDERATIONS

Unless otherwise specified, continuous variables will be summarized by presenting the number of non-missing observations, mean, standard deviation, median, minimum, maximum, 25th percentile and 75th percentile.

Categorical variables will be summarized by presenting the number of subjects and percentage for each category.

All lab values that are reported as “< LLOQ” will be displayed in the listings as received but for summary statistics, this will be imputed as 0.5*LLOQ. For other laboratory values recorded as “< x.x” will be imputed as “x.x” minus 1 or other reasonable handling method as suggested by clinician for calculation.

When appropriate, study days will be listed in the data listings. For each subject, study day is measured relative to the day of study drug administration.

When data are summarized by visit, it will be based on nominal visit as shown on the case report form (CRF), and no date window will be applied. The site will be instructed to complete all assessments required for each study visit according to the schedule of assessments.

Analyses will be performed using SAS for Windows statistical software, version 9.4 or higher (SAS, Cary, NC), except where other software may be deemed more appropriate.

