6.2. Secondary Analysis

6.2.1. CSF Neurotransmitter Analysis

A summary table of descriptive statistics of the observed values, change from baseline and percentage change from baseline will be presented for 5-HIAA, HVA and 3-OMD by time point. A listing for 5-HIAA, HVA and 3-OMD will be provided.

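### The SAP adds t-tests to a descriptive-only protocol without logging them, and the percent-change versions rest on baselines that can be near zero

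*SAP*

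**What the plan says.** Protocol 8.1 says: "This study has no formal statistical hypothesis testing, and the sample size is not based on statistical consideration". For the primary endpoint, Protocol 8.3.2.1 says: "Observed values and change from baseline in HVA at Week 8 will be summarized using descriptive statistics". Protocol 8.3.3 treats the secondary endpoints, PET included, the same way. None of these sections plans a test or a percent change.

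The SAP is written against the same protocol version (V11.0). SAP 6.1 adds: "One-sample t-test will be performed for change and percentage changes from baseline to test whether the changes are statistically significantly different from 0". SAP 6.2.2 adds one-sample t-tests of change and percent change in specific putaminal uptake. SAP 6.2.1 gives no test, but says that "change from baseline and percentage change from baseline will be presented for 5-HIAA, HVA and 3-OMD by time point". SAP 4.4, the section for departures from the protocol's analysis, declares none. The SAP states no significance level or sidedness.

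The estimand in SAP 4.1 is on the absolute scale: "The primary estimand is the change from baseline at Week 8 in HVA for subjects with AADC deficiency".

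On the denominators:

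- **HVA.** Protocol 7.2.1 says that in AADC deficiency "the HVA level in the CSF is very low or below the limit of detection due to the abnormally low dopamine production".
- **5-HIAA.** Protocol 7.3.7 says "the 5-HIAA level is very low or below the limits of detection due to the abnormally low serotonin production".
- **PET.** Protocol 7.3.1 averages the left and right putamen SUVmax, subtracts an occipital SUVmax, and cites one patient in whom no uptake could be measured.

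SAP 4 has two rules for below-limit laboratory values. A result reported as < LLOQ becomes half the LLOQ. Any other value reported as < x.x becomes x.x "minus 1 or other reasonable handling method as suggested by clinician for calculation".

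**The concern.** There are two faults.

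1. A significance test is more than added detail in a plan that says it has no formal testing. With nothing logged in SAP 4.4, anyone relying on that section would conclude that the p-values were always part of the design.
2. A mean of individual percent changes is dominated by the smallest baselines, and the protocol itself expects some baselines to be very small or unmeasurable. For HVA and 5-HIAA, the denominator may then be an imputed number that depends on the rule used. For PET nothing is imputed, but a difference of two maxima can be close to zero or negative, and a negative denominator turns a rise into a negative percent change.

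A percent-change p-value reported under the primary efficacy heading, in a study that may have only three children, could contradict the absolute result for reasons unrelated to treatment.

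**Working it through.** Neither document gives a significance level, an assay limit, HVA units, baseline values or variances, so there is no plan figure to reproduce. All numerical inputs below are assumed, and tests are two-sided at 0.05.

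**1. The two below-limit rules.** For a reporting limit L, the rules give 0.5L and L − 1. They agree only when 0.5L = L − 1, that is, at L = 2.

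| L | 0.5L | L − 1 | % change to a value of 20, 0.5L | % change to a value of 20, L − 1 |
|---|---|---|---|---|
| 5 | 2.5 | 4 | 700 | 400 |
| 2 | 1 | 1 | 1900 | 1900 |
| 1 | 0.5 | 0 | 3900 | undefined |
| 0.5 | 0.25 | −0.5 | 7900 | −4100 |

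**2. Worked HVA example, n = 3.** Baselines are <5, 8 and 12; Week 8 values are 25, 35 and 45. The statistic is t = mean / (SD/√3) on 2 degrees of freedom.

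| Measure | Rule | Individual values | Mean | SD | t | p |
|---|---|---|---|---|---|---|
| Change | 0.5 × LLOQ (2.5) | 22.5, 27, 33 | 27.5 | 5.27 | 9.04 | 0.012 |
| Change | minus 1 (4) | 21, 27, 33 | 27.0 | 6.00 | 7.79 | 0.016 |
| % change | 0.5 × LLOQ (2.5) | 900, 337.5, 275 | 504 | 344 | 2.54 | 0.127 |
| % change | minus 1 (4) | 525, 337.5, 275 | 379 | 130 | 5.05 | 0.037 |

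The rule alone carries the percent-change p-value across 0.05. The 95% CI for absolute change under 0.5 × LLOQ is 27.5 ± 4.303 × 5.27/√3, or about 14 to 41.

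**3. HVA simulation.** There were 40,000 trials per setting. The rise has mean 25 and SD 12; imputed baselines are 2.5 and the others lie between 5 and 30. Entries are the percentage of trials significant.

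| n | Absolute change | % change, none imputed | % change, 10–30% imputed |
|---|---|---|---|
| 3 | 50 | 28 | 13–21 |
| 6 | 98 | 87 | 45–60 |
| 10 | 100 | 99.6 | 87–91 |

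Part of the gap is ordinary ratio variability, as the none-imputed column shows. If every baseline is imputed to the same value, percent change is a rescaled change and the two tests agree. No HVA run was significant in the wrong direction.

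**4. PET simulation.** The variable is the mean of two maxima over 1 cm² minus one maximum over 5 cm², with independent 3 mm voxels: about 100/9 ≈ 11 voxels per putamen region and 500/9 ≈ 56 in the occipital region. The larger region has the higher expected maximum, so with no true uptake the difference is negative on average. There are ten children, and true uptake rises by 6 noise SD in each.

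| True baseline uptake (noise SD) | Absolute test, % significant | % test, significant and correct direction | % test, significant and wrong direction |
|---|---|---|---|
| 0 | 100 | about 0 | about 32 |
| 1 | 100 | about 5 | about 0.2 |
| 2 | 100 | about 70 | none |
| 3 | 100 | about 98 | none |

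At 0.5 SD, wrong-direction significance is about 4%. Across voxel sizes of 2 to 4 mm, correct-direction power at 0, 1, 2 and 3 SD is 0%, 3–10%, 56–82% and 96–99%.

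**The case against.** The strongest reply concerns which below-limit rule covers HVA. SAP 4 applies the subtraction rule only to values not reported as < LLOQ. HVA is a quantitative central-laboratory assay, so half the LLOQ is the natural reading, and the other clause permits a different method in any case. That is fair. The sign reversal is a possibility, not something the SAP mandates. But the protocol speaks of a limit of detection rather than quantification, the SAP never assigns HVA to a rule, and a baseline fixed at half the LLOQ is still a small denominator.

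Second, the SAP already plans medians, quartiles and a listing of the CSF metabolites. In the worked example the median percent change is 337.5% under both rules. This softens the descriptive problem but not the test, which uses the mean.

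Third, the tests are stated openly in SAP 6.1 and 6.2.2, so nothing is concealed from someone who reads those sections. That stands: the fault is an unlogged addition, which SAP 4.4 exists to catch.

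Fourth, the SAP does not define specific putaminal uptake, so equating it with the protocol's SUVmax difference is an inference. SAP 6.2.2 also lists a second uptake variable that the simulation does not cover. The protocol gives the patient without measurable uptake as its reason for using maximal rather than average SUV. Wrong-direction results need baseline uptake near nil across the group. These points limit how firmly the PET figures can be read; they do not make the percent-change test safe.

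**Conclusion.** The concern holds and should be fixed. That testing was added without being logged is plain from the text. The absolute HVA change, which is the primary estimand, is unaffected, and no sample size or success rule depends on these tests.

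The fragility of the percent-change tests follows from the protocol's own description of the baselines. Its size is conditional. For HVA it needs a cohort in which some baselines are near or below the limit and others are not. Under the assumed inputs, power then falls from 50% to 13–21% at n = 3 and from 98% to 45–60% at n = 6, though part of that loss is present with no imputation. For PET it depends on true baseline uptake relative to noise: severe at 0 to 1 noise SD, small by 3. The documents do not allow the actual trial to be placed on either scale.

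**What to change.** - **SAP 6.1 and 6.2.2:** delete the percent-change t-tests.
- **SAP 6.1:** report absolute change in HVA at Week 8 with a 95% CI and each child's values. Label any p-value nominal, and state its level and sidedness.
- **SAP 6.1, 6.2.1 and 6.2.2:** summarise percent change only where the baseline is quantifiable and positive, and state how many children are left out.
- **SAP 4:** use half the reporting limit for every below-limit value, remove the subtraction rule and its open-ended alternative, and report how many baselines were imputed.
- **SAP 4.4:** record that significance testing was added to the protocol's descriptive plan.

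The cost is SAP wording. The sponsor gives up the percent-change p-values. Percent-change summaries will omit the most deficient children and may cover few subjects, so those children must be visible in the individual values. The below-limit change reaches all laboratory variables, which is justified because subtracting 1 gives a zero or negative value at any limit of 1 or less. With three children the interval will be wide, as the 14 to 41 in the example shows.
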